5.2. Number of Participants

A total of approximately 956 patients will be randomized in a 1:1:1:1 ratio:

- 5 mg QW (239 patients),
- 10 mg QW (239 patients),
- 15 mg QW (239 patients),
- insulin glargine QD (239 patients).

5.3. End of Study Definition

End of the study is the date of the last visit or last scheduled procedure shown in the Schedule of Activities (Section 2) for the last patient.

5.4. Scientific Rationale for Study Design

Study GPHO is designed to determine the comparative benefits and risks of once-weekly tirzepatide 5 mg, 10 mg, or 15 mg versus titrated insulin glargine in patients with T2DM who have inadequate glycemic control on stable doses of metformin with or without a sulfonylurea.

An active comparator rather than placebo was selected for this trial because it includes patients with uncontrolled T2DM despite use of oral antihyperglycemic therapies (HbA1c $\geq 7.5\%$ to $\leq 11\%$). Insulin glargine was selected as the comparator because it is a widely used therapy prescribed in this patient population. Metformin and sulfonylurea were chosen as the concomitant antihyperglycemic medication as they are commonly used individually or in combination in clinical practice, and its use in patients who initiate basal insulin therapy has been

applied. To ensure a valid comparison of the randomized study treatments, it is important that insulin glargine is titrated optimally throughout the entire study. Patients will be required to use a TTT algorithm, which has been shown to be effective in enabling a high proportion of patients with T2DM to achieve their therapeutic targets when treated with insulin glargine (Kawamori et al. 2008) as described in Section 7.2.1.2. The frequency of clinic visits postrandomization is intended to allow patients and investigators frequent assessment of study treatments, including optimal insulin glargine dose adjustments as needed for the attainment of glycemic goals within a short time period.

The parallel-group design for treatment comparison was chosen to avoid any interaction between treatments that may interfere with the interpretation of the trial outcome. To minimize the potential confounding effect of changes to concomitant medications, patients will be permitted to use concomitant medications that they require during the study. Medications that may interfere with the assessment of efficacy and safety characteristics of the study treatments will not be allowed (see Section 7.2.1.2). An open-label design was chosen due to the different dosing frequencies, titration scheme of insulin glargine and injection devices compared to tirzepatide.

The planned duration of treatment for the primary endpoint at 40 weeks is considered appropriate to assess the full effects and benefit/risk of each maintenance dose of tirzepatide on both glycemic control and body weight. Moreover, the duration of the study is considered sufficient and appropriate for patients to optimize dosing of insulin glargine for comparison with the tirzepatide treatment groups with respect to change in HbA1c.

5.5. Justification for Dose

Tirzepatide doses of 5 mg, 10 mg, and 15 mg administered subcutaneously QW will be evaluated in this study. These doses and associated escalation schemes were selected based on assessment of safety, efficacy (glycemic and weight loss benefit), and GI tolerability data followed by exposure response modeling of data in T2DM patients in Phase 1 and 2 studies. Dosing algorithms starting at a low dose of 2.5 mg accompanied by dose escalation of 2.5 mg increments every 4-week would permit time for development of tolerance to GI events and are predicted to minimize GI tolerability concerns. The maximum proposed dose of 15 mg maintains an exposure multiple of 1.6 to 2.4 to the no-observed adverse effect level doses in 6-month monkey and rat toxicology studies. The selected dose and escalation scheme would enable further evaluation of benefit/risk considerations for 5 mg, 10 mg, and 15 mg doses of tirzepatide.

This study will be conducted in China and at least 2 other countries/regions and the patient population will predominantly consist of Asian patients. Therefore, this study will use a simple insulin glargine dosing algorithm (refer to Section 7.2.1.2) that has previously been found to be safe and effective in Japanese patients in conjunction with glimepiride, resulting in a steady improvement in glycemic control over 24 weeks without any serious adverse events (Kawamori et al. 2008). However, the frequency of insulin glargine dose adjustments has been altered slightly from the Kawamori schedule, such that it better reflects normal clinical practice in China. In the study by Kawamori et al. (2008), the dose of insulin glargine was adjusted every 2-

3 days, if necessary. In the current study, the dose of insulin glargine will be titrated weekly, with a more intensive follow-up during the first 16 weeks of treatment.

6. Study Population

Prospective approval of protocol deviations to recruitment and enrollment criteria, also known as protocol waivers or exemptions, are not permitted.

6.1. Inclusion Criteria

Patients are eligible to be included in the study only if they meet **all** of the following criteria at screening:

Type of Patient and Disease Characteristics

- [1] Have been diagnosed with type 2 diabetes based on the WHO classification or other locally applicable diagnostic standards

Patient Characteristics

- [2] Are on stable diabetes treatment with metformin with or without a Sulfonylurea (metformin ≥ 1000 mg/day and no more than the maximum approved dose per country-specific label; sulfonylurea should be at least half the maximum dose according to the specific country label information) for at least 2 months prior to Visit 1 and between Visit 1 and Visit 3.
- [3] Are insulin-naive (except for the use of insulin for treatment of gestational diabetes or short-term use [≤ 14 consecutive days] for acute conditions)
- [4] Have HbA1c $\geq 7.5\%$ to $\leq 11.0\%$, as determined by the central laboratory at Visit 1
- [5] Are of stable weight ($\pm 5\%$) ≥ 3 months prior to Visit 1, and agree to not initiate a diet and/or exercise program during the study with the intent of reducing body weight other than the lifestyle and dietary measures for diabetes treatment
- [6] Have body mass index (BMI) ≥ 23 kg/m² at Visit 1
- [7] Are ≥ 18 years old or of an acceptable age to provide informed consent according to local regulations, whichever is older

Male patients (see [Appendix 6](#) for more details):

- Male patients should be willing to use reliable contraceptive methods throughout the study and for at least 3 months after last injection

Female patients:

- Female patients not of childbearing potential due to surgical sterilization (hysterectomy or bilateral oophorectomy or tubal ligation), congenital anomaly (ie. Mullerian agenesis) or menopause.
 - Women with an intact uterus are deemed postmenopausal if they are 45 years old, and

- have not taken hormones or oral contraceptives within the last year and had cessation of menses for at least 1 year,
OR
 - have had at least 6 months of spontaneous amenorrhea with follicle-stimulating hormone (FSH) and estradiol levels consistent with a postmenopausal state (FSH \geq 40 mIU/mL and estradiol $<$ 30 pg/mL).
 - Female patients of child-bearing potential (not surgically sterilized and between menarche and 1-year postmenopausal) must:
 - test negative for pregnancy at Visit 1 based on a serum pregnancy test
AND
 - if sexually active, agree to use two forms of effective contraception, where at least one form is highly effective for the duration of the trial and for 30 days thereafter
 - not be breastfeeding
- [8] In the investigator's opinion, are well-motivated, capable, and willing to:
- a) perform fingerstick BG monitoring, including scheduled BG profiles with up to 7 measurements in 1 day
 - b) learn how to self-inject treatment (tirzepatide or insulin glargine), as required for this protocol (visually impaired persons who are not able to perform the injections must have the assistance of a sighted individual trained to inject the study drug; persons with physical limitations who are not able to perform the injections must have the assistance of an individual trained to inject the study drug)
 - c) are willing and able to inject tirzepatide once-weekly or insulin glargine QD
 - d) maintain a study diary, as required for this protocol.
 - e) have a sufficient understanding of the primary language of the country such that they will be able to complete the patient questionnaires

Informed Consent

- [9] Have given written informed consent to participate in this study in accordance with local regulations and the Ethical Review Board (ERB) governing the study site

6.2. Exclusion Criteria

Patients will be excluded from study enrollment if they meet any of the following criteria at screening:

Medical Conditions

- [10] Have Type 1 diabetes mellitus (T1DM)

- [11] Had chronic or acute pancreatitis any time prior to study entry (Visit 1).
- [12] Have history of:
- proliferative diabetic retinopathy
- or
- diabetic maculopathy
- or
- nonproliferative diabetic retinopathy that requires acute treatment
- (a dilated fundoscopic examination will be performed for all patients between Visit 2 and Visit 3, unless there is a contraindication to dilate the eye [ie. closed angle glaucoma]. The diagnosis will be made by an eye care professional [ophthalmologist or optometrist] before Visit 3 to confirm eligibility)
- [13] Have a history of severe hypoglycemia and/or hypoglycemia unawareness within the 6 months prior to Visit 1
- [14] Have a history of ketoacidosis or hyperosmolar state/coma
- [15] Have a known clinically significant gastric emptying abnormality (for example, severe diabetic gastroparesis or gastric outlet obstruction), have undergone or plan to have during the course of the study: a gastric bypass (bariatric) surgery, or restrictive bariatric surgery (eg, Lap-Band®), or chronically take drugs that directly affect GI motility
- [16] Have any of the following CV conditions within 2 months prior to Visit 1: acute myocardial infarction, or cerebrovascular accident (stroke) or hospitalization due to congestive heart failure (CHF)
- [17] New York Heart Association Functional Classification III and IV CHF
- [18] Have acute or chronic hepatitis, signs and symptoms of any other liver disease other than nonalcoholic fatty liver disease (NAFLD), or alanine aminotransferase (ALT) level >3.0 times the upper limit of the reference range, as determined by the central laboratory at study entry (visit 1); patients with NAFLD are eligible for participation in this trial only if their ALT level is ≤3.0 times the upper limit of normal (ULN) for the reference range
- [19] Have an estimated glomerular filtration rate (eGFR) ≤45 mL/min/1.73 m² (or lower than the country-specific threshold for using the protocol-required dose of metformin per local label), calculated by CKD-EPI, as determined by central laboratory at Visit 1
- [20] Have evidence of a significant, uncontrolled endocrine abnormality (for example, thyrotoxicosis or adrenal crises), in the opinion of the investigator
- [21] Have family or personal history of medullary thyroid carcinoma (MTC) or multiple endocrine neoplasia syndrome type 2 (MEN-2)

- [22] Have a serum calcitonin level of ≥ 35 ng/L (pg/mL), as determined by central laboratory at Visit 1
- [23] Known or suspected hypersensitivity to trial product(s) or related products
- [24] Have evidence of a significant, active autoimmune abnormality (for example, lupus or rheumatoid arthritis) that, in the opinion of the investigator, is likely to require concurrent treatment with systemic glucocorticoids in the next 12 months
- [25] Have had a transplanted organ (corneal transplants [keratoplasty] allowed) or awaiting an organ transplant
- [26] Have a history of an active or untreated malignancy, or are in remission from a clinically significant malignancy (other than basal or squamous cell skin cancer, in situ carcinomas of the cervix, or in situ prostate cancer) for less than 5 years
- [27] Have a history of any other condition (such as known drug or alcohol abuse or psychiatric disorder) that, in the opinion of the investigator, may preclude the patient from following and completing the protocol
- [28] Have any hematological condition that may interfere with HbA1c measurement (for example, hemolytic anemias, sickle-cell disease)

Prior/Concomitant Therapy

- [29] Treatment with any glucose lowering agent(s) other than stated in the inclusion criteria # 2 in a period of 2 months prior to Visit 1 and between Visit 1 and Visit 3
- [30] Have been treated with prescription drugs that promote weight loss (e.g., Saxenda (liraglutide 3.0 mg), Xenical® [orlistat], Meridia® [sibutramine], Acutrim® [phenylpropanolamine], Sanorex® [mazindol], Apidex® [phentermine], BELVIQ® [lorcaserin], Qsymia™ [phentermine/topiramate combination], contrave® [naltrexone/bupropion] or similar other body weight loss medications including over-the-counter [OTC] medications [e.g., alli®]) within 3 months prior to Visit 1 and/or between study entry (Visit 1) and randomization (Visit 3)
- [31] Are receiving chronic (>2 weeks or 14 days) systemic glucocorticoid therapy (excluding topical, intra-ocular, intranasal, or inhaled preparations) or have received such therapy within 1 month of Visit 1; or between Visits 1 and 3

Prior/Concurrent Clinical Trial Experience

- [32] Are currently enrolled in any other clinical study involving an investigational product or any other type of medical research judged not to be scientifically or medically compatible with this study

- [33] Have participated, within the last 30 days in a clinical study involving an investigational product. If the previous investigational product has a long half-life, 5 half-lives or 30 days (whichever is longer) should have passed
- [34] Have previously completed or withdrawn from this study or any other study investigating tirzepatide

Other Exclusions

- [35] Are investigator site personnel directly affiliated with this study and/or their immediate families. Immediate family is defined as a spouse, parent, child, or sibling, whether biological or legally adopted
- [36] Are Lilly employees
- [37] Are unwilling or unable to comply with the use of a paper diary to directly record data from the subject

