will receive a glucometer, study diaries and training on how to perform self-monitoring of blood glucose (SMBG) and record BG values, hypoglycemic events, medications and adverse events. Patients will be provided diaries and will be trained as appropriate to record BG values, hypoglycemic events. During this period, patients should be on a stable dose of metformin (≥ 1000 mg/day and no more than the maximum approved dose per country-specific label) with or without a sulfonylurea (at least half of the maximum approved dose per country specific label). Patients will also be trained on disease management and study procedures; this training can be repeated at subsequent visits as deemed appropriate. If patients develop a condition that is a contraindication for the use of OAMs, they will be considered ineligible and must be discontinued from the trial before randomization.

Study Period II (40-week treatment period)

Randomization (Visit 3)

At Visit 3, eligible patients will perform all required baseline study procedures (including the collection of all baseline laboratory measures and ECG) prior to randomization and prior to taking the first dose of study drug. Patient should arrive to the clinic in the fasting state; the fasting state should have lasted at least 8 hours without having taken any doses of their study drug, metformin and sulfonylurea (if used). The questionnaires (European Quality of Life [EQ-5D-5L], Ability to Perform Physical Activities of Daily Living [APPADL], Impact of Weight on Self-Perception [IW-SP], and Diabetes Treatment Satisfaction Questionnaire status [DTSQs]) should be completed before any other study procedures if the patient is not adversely affected by the fasting condition or completed after the patient has sufficiently recovered from the preceding visit procedures.

Patients assigned to tirzepatide will be instructed on how to use the single-dose pen (SDP) and will inject their first dose of tirzepatide while in the clinic for Visit 3. Patients randomized to the insulin glargine group will be trained on how to use the prefilled pen and will administer insulin glargine once daily ideally at bedtime. The date and time of the first dose of tirzepatide and the date of the first dose of insulin glargine should be recorded on the electronic case report form (eCRF).

Following randomization, patients will participate in a 40-week treatment period.

Postrandomization period (end of Visit 3 to Visit 19):

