8.1. Discontinuation from Study Treatment

8.1.1. *Permanent Discontinuation from Study Treatment*

Possible reasons leading to permanent discontinuation of investigational product:

- **Patient Decision**
 - The patient requests to discontinue investigational product.
- **Discontinuation due to a hepatic event or liver test abnormality.** Patients who are discontinued from investigational product due to a hepatic event or liver test abnormality should have additional hepatic safety data collected via the electronic case report form (eCRF).

Discontinuation of the investigational product for abnormal liver tests **should be** considered by the investigator when a patient meets one of the following conditions after consultation with the Lilly designated medical monitor:

- ALT or aspartate aminotransferase (AST) >8X ULN
- ALT or AST >5X ULN for more than 2 weeks
- ALT or AST >3X ULN and total bilirubin level (TBL) >2X ULN or international normalized ratio (INR) >1.5
- ALT or AST >3X ULN with the appearance of fatigue, nausea, vomiting, right upper-quadrant pain or tenderness, fever, rash, and/or eosinophilia (>5%)
- alkaline phosphatase (ALP) >3X ULN
- ALP >2.5X ULN and TBL >2X ULN
- ALP >2.5X ULN with the appearance of fatigue, nausea, vomiting, right quadrant pain or tenderness, fever, rash, and/or eosinophilia (>5%)

In addition, patients will be discontinued from the investigational product in the following circumstances:

- If a patient is inadvertently enrolled and it is determined that continued treatment with study drug would not be medically appropriate, see Section [8.1.3](#)
- Acute or chronic pancreatitis
- If a patient is diagnosed with MTC after randomization, or has a postrandomization calcitonin value ≥ 35 ng/mL that has increased at least 50% over baseline
- If a patient is diagnosed with an active or untreated malignancy (other than basal or squamous cell skin cancer, in situ carcinomas of the cervix, or in situ prostate cancer) after randomization
- Any significant study drug-related hypersensitivity reaction

- Any other TEAE, SAE, or clinically significant laboratory value for which the investigator believes that permanent study drug discontinuation is the appropriate measure to be taken
- If female patient becomes pregnant
- If a patient is diagnosed with T1DM

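### The pancreatitis, severe-hypoglycemia and cardiovascular event exclusions stop at Visit 1, so an event in the roughly 3-week lead-in is not by itself a reason not to randomize

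*Protocol*

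**What the plan says.** Protocol Section 6.2 applies its list as follows: "Patients will be excluded from study enrollment if they meet any of the following criteria at screening". Three criteria defined by medical events carry an explicit end point at Visit 1:

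- [11]: "Had chronic or acute pancreatitis any time prior to study entry (Visit 1").
- [13]: "Have a history of severe hypoglycemia and/or hypoglycemia unawareness within the 6 months prior to Visit 1".
- [16]: "Have any of the following CV conditions within 2 months prior to Visit 1", followed by acute myocardial infarction, stroke and hospitalization for congestive heart failure.

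Protocol Section 7.2 places randomization at Visit 3. The Schedule of Activities puts Visit 1 at Week -3 and Visit 3 at Week 0, with a window of 7 days either way for Visit 3.

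Other criteria name the interval up to Visit 3. Exclusion [30], on weight-loss drugs, applies "within 3 months prior to Visit 1 and/or between study entry (Visit 1) and randomization (Visit 3"). Inclusion [2] and exclusions [29] and [31] also cover Visit 1 to Visit 3. Exclusion [12] is confirmed by an eye examination before Visit 3.

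For the lead-in, Protocol Section 5.1 adds: "If patients develop a condition that is a contraindication for the use of OAMs, they will be considered ineligible".

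**The concern.** Events of these kinds are disqualifying before Visit 1 but are not named as disqualifying in the weeks just before the first dose. An exclusion meant to keep out patients with a recent serious event would be expected to cover the most recent period as well. At stake are the safety of a small number of patients who could start tirzepatide or insulin glargine soon after such an event, and uniform handling across sites: two investigators could treat the same lead-in event differently and both be within the protocol.

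**Working it through.** The plan states no figure on this point, so the check is one of dates and wording.

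**Length of the uncovered interval** (Schedule of Activities):

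- Nominal: Week 0 minus Week -3 = 3 weeks; 3 × 7 = 21 days.
- With the Visit 3 window: 21 − 7 = 14 days to 21 + 7 = 28 days.

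**Where each criterion ends:**

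- [11] pancreatitis: starts at any earlier time, ends at Visit 1.
- [13] severe hypoglycemia or unawareness: starts 6 months before Visit 1, ends at Visit 1.
- [16] myocardial infarction, stroke, heart-failure hospitalization: starts 2 months before Visit 1, ends at Visit 1.
- [2] stable oral therapy and [29] other glucose-lowering agents: start 2 months before Visit 1, end at Visit 3.
- [30] weight-loss drugs: starts 3 months before Visit 1, ends at Visit 3.
- [31] chronic systemic glucocorticoids: starts 1 month before Visit 1, ends at Visit 3.

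**Worked case for [16].** A stroke 8 weeks before Visit 1 lies 56 + 21 = 77 days before nominal randomization and is excluded. A stroke 7 days before randomization falls 21 − 7 = 14 days after Visit 1 and does not meet [16].

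**Does the application time close the gap?** Protocol Section 5.1 separates screening (Visit 1) from the lead-in (Visit 2 to Visit 3), and SAP Section 5.1 says that eligibility apart from retinopathy status is established at Visit 2. Even if screening meant the whole of Study Period I, the Visit 1 end points inside [11], [13] and [16] would still govern.

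**Do other rules cover these events?**

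- [29] applies if insulin or another agent outside [2] is given in the lead-in; [2] applies if metformin is interrupted. Both depend on how the event is treated.
- [17] depends on NYHA class III or IV, not on an admission.
- [27] rests on the investigator's opinion about following and completing the protocol.
- The lead-in rule in Section 5.1 depends on whether the event contraindicates an oral agent, which turns on country labels that the documents do not give.
- Section 8.2 allows participation to stop for medical or safety reasons, by judgment.
- Section 8.1.3, on inadvertent enrollment, is for patients who failed the criteria. A patient whose only issue is such a lead-in event has not failed them as written.

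None of these makes the event itself a bar to randomization.

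**Is the information available in time?** Yes. The Schedule of Activities collects adverse events and hypoglycemic events at Visits 1, 2 and 3.

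**The case against.** The best reply is that the gap is narrower than the three criteria suggest. A patient admitted with a stroke, infarction or pancreatitis may well receive insulin or have metformin stopped, and would then fail [29] or [2]. Section 7.4.2 itself lists severe dehydration, surgery and iodinated contrast as reasons to interrupt metformin. Investigators are responsible for medical care, and many would withhold randomization. All this stands and limits the number of patients affected, but it does not make the written criteria cover the events.

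One may also say that fixing medical status at Visit 1 while requiring stable therapy to Visit 3 is a recognizable design, since [4], [5], [6], [18], [19] and [22] also refer to Visit 1. That has some force, and the documents do not show whether the Visit 1 end points were intended. But those criteria rest mainly on measurements taken at Visit 1 or on weight stability before it, whereas [11], [13] and [16] concern events that can newly occur during the lead-in.

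Four stronger readings are tempting and are not supported:

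- **That the oral-agent rule is the only ineligibility rule in the lead-in.** It is not. The eye examination, the urine pregnancy test required before randomization, and [2], [29], [30] and [31] also operate there.
- **That [11] contradicts Section 8.1.1, which lists "Acute or chronic pancreatitis" among the reasons to discontinue investigational product.** An entry criterion and a stopping rule do different jobs, and both can be followed.
- **That affected patients would drop out of the efficacy analysis set.** SAP Table GPHO.6.1 removes data after rescue or study drug discontinuation (last dose date plus 7 days), not patients.
- **That the uncovered days, as a share of a look-back period, measure the risk.** Such a share is calendar arithmetic, differs between [13] and [16], and cannot be formed for [11], which has no start date.

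**Conclusion.** The point holds as a gap in eligibility wording. For nominally 21 days before randomization (14 to 28 with the Visit 3 window), pancreatitis, severe hypoglycemia or unawareness, myocardial infarction, stroke or heart-failure hospitalization is not by itself a reason not to randomize, although the therapy criteria cover those same days.

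The consequence is for patient safety and for uniform application of the criteria. The documents give no event rates, so the number of patients cannot be computed; that it would be small is an expectation. A reader might infer harm to the trial's inference. Nothing in the documents supports that: no effect on power, type I error or the primary estimate is shown, and randomization would spread such patients over the arms without a systematic difference in expectation.

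The conclusion rests on the nominal visit schedule and on reading the Visit 1 end points literally. It takes no position on how long the look-back periods should be.

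**What to change.** Reconcile the end point of [11], [13] and [16] with that of [29] to [31]. One way is to add the Visit 1 to Visit 3 wording that [30] already contains; if the sponsor intended the Visit 1 end points, the protocol should say so and give the reason. The start of each look-back can stay as it is. Add an eligibility confirmation at Visit 3, before the interactive web-response system is used, drawing on the adverse event and hypoglycemia records already collected.

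The cost is a protocol wording change, one line on the Visit 3 checklist and a very small number of additional pre-randomization failures. No new procedure, sample size change or SAP analysis is needed.
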